6.6.2. Clinical Laboratory Assessments

Laboratory data will be presented as per the international system of units, universally abbreviated as SI (from the French ‘system international’).

Hematology and blood chemistry will be summarized using descriptive statistics by treatment group and visit. Change from baseline values will be summarized similarly by treatment group for each post-baseline scheduled visit. Number and percentage of subjects with urine pregnancy test will be provided by treatment group and visit.

Shift tables from baseline to post-baseline for hematology and blood chemistry assessment, describing shifts to abnormality (low, normal, or high), will be provided. The number of subjects with a non-missing result at both baseline and a specific post-baseline scheduled visit will be used as denominator for that post-baseline scheduled visit.

Separate listings of all hematology, blood chemistry and urine pregnancy data will be provided. In addition, separate listings for hematology, blood chemistry, and urine pregnancy data will be provided for each parameter where a subject had at least one abnormal result.

All laboratory tests required at screening and/or baseline only will be listed.

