14.7. Safety Laboratory Tests

Safety laboratory tests will be performed by a qualified local laboratory. Samples for safety laboratory tests will be collected at the Screening, TOC, and at any unscheduled visit, if needed. If indicated, these may be done more frequently as follow up to a laboratory abnormality.

The following laboratory parameters will be determined:

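### The SAP's laboratory shift and change tables use scheduled visits only, so transient or for-cause abnormalities in on-schedule Cycle 1 subjects are counted in no shift table

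*SAP*

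**What the plan says.** SAP 6.6.2 plans three kinds of laboratory table.

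- Observed values: "Hematology and blood chemistry will be summarized using descriptive statistics by treatment group and visit". This sentence does not restrict the visits to scheduled ones.
- Change from baseline: "Change from baseline values will be summarized similarly by treatment group for each post-baseline scheduled visit".
- Shift tables, "describing shifts to abnormality (low, normal, or high), will be provided", with this rule: "The number of subjects with a non-missing result at both baseline and a specific post-baseline scheduled visit will be used as denominator".

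It also plans listings. "Separate listings of all hematology, blood chemistry and urine pregnancy data will be provided", and further listings "will be provided for each parameter where a subject had at least one abnormal result". SAP 6.7 adds a profile for every subject. The section describes no worst-value or any-time shift, and gives no rule for placing unscheduled or early-termination results in the change and shift tables.

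On sampling, Protocol 14.7 says: "Samples for safety laboratory tests will be collected at the Screening, TOC, and at any unscheduled visit, if needed". It adds: "If indicated, these may be done more frequently as follow up to a laboratory abnormality". Table 1 and Protocol 18.7.1 agree that TOC is the only scheduled post-baseline laboratory visit. Protocol 18.7.2 promises reference-range shifts from Baseline by treatment group and does not limit them to scheduled visits; that limit is added by the SAP.

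**The concern.** Safety laboratory tests are a named safety measure (Protocol 9.2, SAP 4.2.2). A shift table is where a reader looks for the proportion of subjects in each arm who moved outside the reference range. Here it rests on one time point per cycle. In Cycle 1 that time point comes after dosing has ended for anyone who follows the schedule, and the interval since dosing differs by regimen.

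The samples taken at other times are the unscheduled ones, drawn because something was suspected or to follow an abnormality already seen. These are the samples most likely to show a problem, and the shift and change tables have no place for them. A table could therefore show no shifts in an arm where abnormal values were measured and are in the database.

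The three-level scale causes a second, smaller loss. A subject already above range at baseline who rises further is recorded as high to high. Group B can include subjects with diabetes, HIV or immunosuppressive therapy, so abnormal baselines are plausible, although the documents give no frequency.

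**Working it through.** The documents contain no figure to reproduce here. The check is day arithmetic, followed by tracing cases through the stated tables.

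**Inputs**

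- TOC is 14 ± 3 days after Baseline, and Baseline is Day 1 (Protocol 10.1.1).
- Cycle 1 dosing lasts 1, 3 or 7 consecutive days from Day 1 (Protocol 12.1).
- Doses are about 12 ± 3 hours apart, and a first dose at 8 p.m. at home is allowed (Protocol 14.15).
- Cycle 2 dosing lasts up to 14 days (Protocol 12.1), on the same visit schedule starting at Baseline (Protocol 15).
- The planned arm size is 50 (Protocol 18.1, SAP 5.4).

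**Days from last dosing day to TOC**

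TOC day = 1 + 14 ± 3, so Day 12 to Day 18. Interval = TOC day − last dosing day.

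| Regimen | Last dosing day | Earliest TOC | Latest TOC |
|---|---|---|---|
| 1 day | 1 | 12 − 1 = 11 | 18 − 1 = 17 |
| 3 days | 3 | 12 − 3 = 9 | 18 − 3 = 15 |
| 7 days | 7 | 12 − 7 = 5 | 18 − 7 = 11 |
| Cycle 2, 14 days | 14 | 12 − 14 = −2 | 18 − 14 = 4 |

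**How firm the 7-day minimum is**

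- Evening start, 12-hour spacing: the 14th dose falls 20 + 13 × 12 = 176 hours after midnight at the start of Day 1. Since 176 = 7 × 24 + 8, that is 8 a.m. on Day 8. The minimum becomes 12 − 8 = 4 days.
- TOC window read as study Day 14 ± 3 (Days 11–17): 11 − 7 = 4 days, or 11 − 8 = 3 with the evening start.
- Evening start with every interval at the 15-hour limit: 20 + 13 × 15 = 215 hours, which is 11 p.m. on Day 9. A TOC at 8 a.m. on Day 12 (an assumed clock time) is at 11 × 24 + 8 = 272 hours. The gap is 272 − 215 = 57 hours, about 2.4 days.

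Under each of these readings an on-schedule Cycle 1 TOC falls after the last dose. In Cycle 2 with 14 days of dosing it can fall up to 2 days before the last dosing day.

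**Tracing cases through the SAP 6.6.2 tables**

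| Case (one parameter) | Shift table at TOC | Other places it can appear |
|---|---|---|
| Baseline normal, unscheduled Day 5 high, TOC normal | normal to normal | listings, profile, possibly observed values, adverse event if declared |
| Baseline normal, TOC normal, unscheduled value after TOC high | normal to normal | as above, with adverse event recording after TOC restricted |
| Baseline high, TOC several times higher | high to high | maximum of the change-from-baseline summary, listings, adverse event if declared |
| Baseline normal, abnormal at Day 5 and still at TOC | normal to high | captured |
| Discontinues during dosing, TOC procedures done then | captured if the sample is assigned to TOC | assignment rule not stated |

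**Size per case**

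One uncounted subject in an arm of 50 lowers the tabulated incidence by 1/50 = 2 percentage points. The number of such subjects cannot be derived, because the documents give no expected number of unscheduled samples.

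**The case against.** The strongest reply is that these results are not lost. Protocol 16.1 makes any laboratory abnormality that the investigator considers clinically significant an adverse event, and SAP 6.6.1 counts treatment-emergent events by treatment group, by severity and by relationship. A marked rise on Day 5 should reach those tables. The observed-value summary is not restricted to scheduled visits. All values and all abnormal values are listed. SAP 6.1 includes the minimum and maximum among the descriptive statistics, so a large rise at TOC from a high baseline shows as an extreme change. The low/normal/high scale follows the protocol's own reference-range specification. The study is exploratory with no formal safety analysis, and the mock tables are in a separate document not available here.

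Most of this stands, and it rules out three stronger readings that a reader might infer.

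- That such abnormalities are missing from every summary. They are not: declared ones are counted as adverse events, and the observed-value table may include them.
- That no scheduled laboratory sample is ever taken on drug. Protocol 11.3, 11.4 and 18.4 call for TOC procedures, or TOC information, at early discontinuation, when additional antifungal therapy is given before TOC, or at withdrawal. Such a sample can fall during or just after dosing, as can a Cycle 2 TOC.
- That Cycle 1 tables show only recovered values. The documents give no half-life and no time course for laboratory effects, and an abnormality present at TOC is tabulated.

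The reply does not close the gap. Means and extremes do not count subjects who left the reference range. Listings and profiles give no rate by arm. Adverse event counts depend on the investigator's judgment of significance in an open-label study. After TOC, Protocol 16.9 limits new adverse events to those that led to antifungal or topical vaginal treatment, those that are vaginal bacterial or parasitic infections, and those judged related. A non-serious worsening after TOC that is judged unrelated can therefore miss both the adverse event tables and the shift tables. The unseen mock tables may be better than the text, but the SAP's stated denominator is what a programmer would follow.

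**Conclusion.** The point holds for the change and shift tables, and for Cycle 1 subjects who stay on schedule. In these subjects a transient or for-cause abnormality found at an unscheduled visit is counted in no laboratory shift table. Their one tabulated post-baseline value is taken nominally 11–17, 9–15 or 5–11 days after the last dosing day, with a minimum of about 4 days on the 7-day regimen after an evening start at 12-hour spacing. Because the interval differs between the 3-day and 7-day arms, the by-visit tables also compare the two randomized regimens at different times since dosing.

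The size of the loss is unknown. A reader might take 2 percentage points as the expected bias; it is only the effect of one missed subject in an arm of 50, and the number missed could be zero.

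The conclusion assumes that the SAP text governs over mock tables not seen here, and that unscheduled results are not reassigned to TOC by a rule outside the SAP. It is a reporting gap with a cheap remedy. It does not touch the efficacy analysis or the collection of safety data.

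**What to change.** In SAP 6.6.2, add the following and keep the by-visit tables.

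- A shift table per parameter and cycle from baseline to the worst post-baseline value, using all scheduled, unscheduled and early-termination samples. The denominator is every subject with a baseline and any post-baseline result in that cycle. For parameters where both directions matter, show the lowest and the highest value separately. Use the Cycle 2 baseline already defined in SAP 6.1.1.
- For key chemistry (for example liver tests, bilirubin, CPK and creatinine), categories by multiple of the local laboratory's upper limit of normal, so that worsening from a high baseline is visible.
- A sentence stating how early-termination laboratory results are assigned to a visit in the by-visit tables.
- The number of subjects with unscheduled samples in each arm, because a worst-value table depends on how often subjects are sampled.

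The cost is one or two extra tables from data already collected, with no new visit or procedure. For-cause samples may make the reported incidence slightly less favourable.

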6.6.3. Physical Examinations and Clinical Assessment of Signs and Symptoms

Physical Examination will be presented in a subject listing, with abnormal values flagged and abnormal description listed if any. Clinical assessment of signs and symptoms at each visit will be summarized and listed by subject.

6.7. Patient Profile

Patient profile will be provided for all subjects. Please refer to the separate patient profile sample document.

7. APPENDIX 1: VULVOVAGINAL SIGNS AND SYMPTOMS SCALE

SIGNS:

To be rated by the investigator during the vulvovaginal examination

| Sign | Absent 0 | Mild 1 | Moderate 2 | Severe 3 |
|--------------------------------|-------------|-----------|---------------|-------------|
| Edema | | | | |
| Erythema | | | | |
| Excoriation or fissures | | | | |

- Definitions: Absent: none Mild: slight
- Moderate: definitely noticeable Severe: marked, intense

SYMPTOMS:

To be rated by the subject

| Symptom | Absent 0 | Mild 1 | Moderate 2 | Severe 3 |
|-------------------|-------------|-----------|---------------|-------------|
| Burning | | | | |
| Itching | | | | |
| Irritation | | | | |

Definitions:

[figure not shown]
- Absent: I have no discomfort (i.e., burning, itching, irritation)
- Mild: I have some discomfort (i.e., burning, itching, irritation), but it does not bother me much
- Moderate: I have discomfort (i.e., burning, itching, irritation), which is annoying, but not enough to affect what I am doing
- Severe: I have discomfort (i.e., burning, itching, irritation), which is annoying enough to affect what I am doing

8. APPENDIX 2: QUALITY OF LIFE

[figure not shown]
8.1. SECTION 1

The following questions ask about your VVC symptoms and their impact on your overall wellness. Please indicate with a cross on the line below how you would rate your symptoms over the past 7 days.

[figure not shown]
1. How would you rate your vaginal itching over the past 7 days?

[figure not shown]
2. How would you rate your vaginal burning over the past 7 days?

[figure not shown]
3. How would you rate your vaginal irritation over the past 7 days?

4. How would you rate your vaginal discharge over the past 7 days?

5. How would you rate your pain or discomfort during urination over the past 7 days?

6. How would you rate your pain or discomfort during sexual intercourse over the last 7 days?

0 1 2 3 4 5 6 7 8 9 10

Δ Not Applicable (N/A)

[figure not shown]
No pain or
discomfortExtreme pain or
discomfort

7. To what extent have your VVC symptoms affected your willingness to engage in sexual intercourse over the last 7 days?

0 1 2 3 4 5 6 7 8 9 10

Δ Not Applicable (N/A)

8.2. SECTION 2

The following questions ask about changes in your life related to your VVC symptoms since beginning this study. Please check the box next the number that best describes your experience.

9. Since beginning this study, how would you describe the change in your overall sexual satisfaction related to your VVC?
